6.4 Approved Contraception

Females of child-bearing potential who engage in heterosexual intercourse during the trial must utilize one of these approved methods for contraception:

- Oral Hormonal Contraception
- Patch Contraception
- Hormonal Ring
- Intrauterine Device (IUD)
- Contraceptive Implantation
- Contraceptive Shot
- Barrier Method, including:
 - Male Condom
 - Female Condom
 - Diaphragm
 - Cervical Cap with spermicide
 - Contraceptive Sponge
 - Spermicide

6.5 Screen Failures

Participants who fail the initial screening process will be notified as soon as the screen failure is recognized. Participants that failed the screening process due to failing to meet the inclusion

criteria or meeting exclusion criteria may be rescreened at a later date if the reason for their original exclusion no longer applies, or if a protocol amendment changes the eligibility criteria that caused the original screen failure. A minimum of 30 days should occur between re-assessing eligibility, and participants can re-screen with the original Participant ID. However, participants that were excluded due to cognitive screening scores out of range (i.e., MMSE > 25 or <15) or demonstrated evidence of suicidality on the C-SSRS at the original screening will not be permitted to rescreen.

6.6 Strategies for Recruitment and Retention

The majority of participants for the study are expected to be drawn from existing patient populations at the clinical sites/services after medical record review. However, sites may choose to utilize recruitment aids such as IRB-approved advertisements.

The Sponsor will assign a Clinical Research Associate (CRA), also known as a study monitor, to each site. Enrollment for each site will be closely monitored by the CRA via Pre-screening logs that will be reviewed on a regular basis. If needed, the CRA will work closely with the site to identify recruitment barriers and find solutions to overcome these hurdles.

A variety of strategies are being utilized to avoid unnecessary attrition. The study design facilitates retention as there are only 4 visits requiring travel to the study center, and care was taken to reduce study visit length of time, thereby reducing participant and caregiver burden. Additionally, participants and study partners will receive stipends to compensate for the travel and time burden associated with participation in the study. Participant retention will also be closely monitored, and the CRA will work with the site to identify solutions should retention issues arise.

7. Study Intervention

Intended Use: The TNM™ Device is intended to stimulate the vestibular system via external ear canals using software-controlled thermal waveforms.

7.1 Study Intervention Administration

The generation 3.2 TNM™ device was granted market entry by the FDA as a Class II medical device indicated for the home-use prevention of episodic migraine in adolescent and adult patients 12 and older.

The generation 4.0 Device will be utilized in this study. See Scion TNM™ 4.0 Investigator Brochure for more details. The Sponsor has designated this Device as non-significant risk (NSR) for participants with PD and PDD.

For treatment, all participants will recline on a wedge pillow (provided by SNS) to position the horizontal semicircular canal in the optimal orientation for maximal caloric effect. Participants will start and stop the device with a single push button to activate a run. Starting and stopping the device requires an extended push (2 seconds) to avoid false activations due to short button pushes. The LED display provides a “countdown” icon to provide the participant with feedback on how the treatment session is proceeding. The display also tells the participant how many treatments are left within the prescription period. The device provides an audio alert that denotes the start and completion of a treatment run.

Device treatment does not require active engagement of the participant. Therefore, participants

will be told that they should feel free to read, watch television or rest so long as they remain in the supine position for the duration of treatment. Participants may be provided items to make the treatment time more conducive to reclining leisure activities such as reading, watching tv, etc. An example of such an item would be prism glasses to enable reading, if desired, while lying supine during a treatment.

Participants will be asked to treat twice daily. Each treatment duration is roughly 19 minutes and treatments must be separated by at least 1 hour. Participants will only wear the device when administering a treatment. Participants will be encouraged to self-administer treatments in the on-state and at a time when they do not anticipate interruptions that would require them to pause treatment.

All participants will be told that they may or may not benefit from device therapy in terms of reduction in PD-related symptoms. All participants will be told that participants may or may not sense slight pressure from the earpieces, a warming or cooling sensation, slight nausea or dizziness or noises from the Device. To mitigate risk of falls that may result from orthostatic hypotension, participants will be instructed to take their time getting up after a treatment and to avoid going directly from a supine position to standing up and moving around.

7.2 Preparation/Handling/Storage/Accountability

Study devices must be stored in a secure area with limited access. Storage rooms used for this purpose must have continuous locked access and only delegated research staff should be allowed to enter.

Upon receipt, the shipment of study devices will be inventoried. Any discrepancies or damaged shipments will be brought to the attention of the sponsor. Copies of the packing slips will be retained, and inventory will be documented on the Investigator Inventory Control Form located in the Investigator Site File for the study. The Sponsor and the Investigator are required to closely monitor the shipping, use, and final disposal of devices.

Investigators must also maintain complete, current, and accurate records of the receipt, use, or disposition of investigational devices. Delegated research staff should complete the Investigator Inventory Control Form whenever one of the following occurs: 1) devices are received from the Sponsor, 2) devices are dispensed to participants, 3) devices are returned from participants and 4) devices are shipped back to the Sponsor. In the case of a damaged or failed device, an Investigational Device Return Form should be completed, and the Sponsor immediately notified.

Upon completion or termination of the study (or the Investigator's part of the study), or at the sponsor's request, the Investigator is required to return to the Sponsor any remaining supply of the device, unless otherwise directed.

7.3 Device Allocation

The Generation 4.0 TNM™ device uses a bar code reader to import a prescription waveform and the QR code is not readable by staff members. Bar codes will be printed on plastic ID cards.

After eligibility is confirmed and documented and the participant has confirmed comfort of the device after trying it on, delegated study staff will scan the bar code. Study staff will load the treatment onto the device, record the device number allocated to the participant and will train the

participant according to the training script provided. The first treatment will be performed at the study site to confirm understanding of the training by the study participant and study partner, and subsequent confirmation of understanding at the next visit will also occur.

Participants will be told that pain should not be associated with treatment, and if they do experience pain, that they should stop treatment and contact the study staff immediately and/or seek medical attention if necessary.

7.4 Study Intervention Adherence

The actual, measured temperature profile for each run will be automatically saved to Device memory, as will the time and date of each treatment run. These data will be accessible via a USB port that is covered by a hatch on the device body and will be downloaded by SNS. This data is an independent record of the expected device performance and treatment adherence and will be used for confirmation purposes and planned analyses, not for confirming adherence in real time. Study participants will not be withdrawn by the study staff for significant treatment non-adherence.

8. Study Intervention Discontinuation and Participant Discontinuation/Withdrawal

8.1 Discontinuation of Study Intervention

All AEs will be evaluated by site personnel on an individual basis to determine whether the occurrence may be related to device use. Any issues related to safety concerns will promptly be referred to the site principal investigator, who can terminate the participant's further participation in the study if necessary.

Should a serious adverse event occur that is deemed to be likely related to device use, the potential for the universality will be assessed within 48 hours. If evidence suggests that treatments with the device could create a safety concern for participants, as deemed by the medical monitor, the study will be paused or stopped early, as appropriate.

It should be noted that the above scenario is considered to be highly unlikely. The device has been designated as NSR by the Sponsor, and there were no reports of serious or unexpected AEs that were potentially related to device in either the PD single-site RCT or the episodic migraine RCT.

8.2 Lost to Follow-Up

8.2.1 Withdrawal Criteria

Participants must be withdrawn from the clinical trial if any of the following events occur:

- the participant is significantly non-adherent to the requirements of the protocol (principal investigator & Sponsor decision, of note requirements relate to participation and completion of activities during study visits and do not include adherence of treatments with the study device),
- the participant develops an illness or condition that would interfere with his/her continued participation,
- the participant withdraws his/her consent,
- the participant's study partner withdraws his/her consent and no replacement can be found

Clinician version – not for patient use

- the principal investigator feels that it is the participant’s best interest to be withdrawn,
- the participant and/or their study partner is unable to demonstrate device use at the required visits
- SNS discontinues the study or has achieved the targeted enrollment,

If the participant is discontinued from the participation in the study for any reason, the principal investigator must make every effort to perform all evaluations for the final visit, even virtually, if necessary, collect the device from the participant and document the reasons for discontinuation. If the participant withdraws from the study due to an adverse event that is potentially related to use of the device, the study staff should continue to follow up with the participant at regular intervals, and at least every two weeks until the AE resolves or until the participant withdraws consent for the follow-up procedure.

If a participant’s study partner withdraws their consent from the study, a new study partner who meets the criteria may be identified and consented to the study. If a suitable study partner cannot be found, the participant will be withdrawn from the study.

Participants that withdraw early will be excluded from the per protocol analysis.

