--	---

SHARPEN, V3.0 -- CONFIDENTIAL

Clinician version – not for patient use

	
12. Have active ear infections, perforated tympanic membrane or labyrinthitis, as identified by a general ear examination performed by medically qualified Investigators or have chronic tinnitus that has been ongoing for at least 3 months.
 
13. Have a cochlear implant, myringotomy tubes or hearing aids that cannot be easily/reliably removed for treatment.
 
14. Clinically significant abnormalities in B12, thyroid function, blood count, comprehensive metabolic panel or urinalysis results tested at the study screen. Screening tests are not required in cases where test results within normal range within 6 months of study screen are documented in the medical records.

Sample Size	
This study will enroll participants until 12 participants have received at least one (1) treatment with the TNM™ Device prior to competitive enrollment closing. Both intention-to-treat (ITT) and per-protocol (PP) data will be analyzed.

Clinical Sites	
The study will be conducted at approximately 2 study centers in the United States. The sites will include movement disorder specialty clinics and academic centers. All sites will have the expertise in the conduct of clinical trials for Parkinson’s disease therapeutics and documentation of staff training for all clinical assessments.

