Device dispensation will occur only after all scheduled assessments and activities have been completed. The participant and study partner will be trained on how to use and care for the Device. The participant (with the assistance of the study partner as appropriate) should complete the first treatment administration at the study site to demonstrate to study staff an understanding of how to set-up, use, and clean the study Device. The participant will then take the study Device home, treat once more for the day, and continue with twice daily treatments for the duration of the treatment period.

Treatment Period: The 12 weeks (~84 days) following the pre-treatment baseline period constitute the treatment period. Participants will self-administer treatments twice daily with at least an hour in between treatment sessions, for the full treatment period up until the scheduled end of treatment visit. Treatment adherence will be recorded by the Device.

Phone contact (Day 1, +/- 1 day)

The first day (Day 1) after Device allocation, the study staff should contact the participant/study partner to confirm that treatments have been administered, that there are no questions or concerns about the Device and to review concomitant medications and potential adverse events.

Early Treatment Period Visit 1 - day 3 (+/- 3 days): *This in-clinic visit may be completed virtually at the participant and study partner's request if the customized cognitive battery does not need to be collected.* The participant and study partner should return to the clinic with the study device. The study participant (with the assistance of the study partner as

SHARPEN, V3.0 -- CONFIDENTIAL

Clinician version – not for patient use

appropriate) should complete a treatment administration at the study site to demonstrate to study staff an understanding of how to use the study Device. If participants and their study partners do not meet the criteria specified in the Treatment Administration Verification Form, the participant and study partner will be re-trained on how to use and care for the Device. The participant will then take the study Device home, treat once more for the day, and continue with twice daily treatments for the duration of the treatment period.

CCB (if not collected at the Baseline day 0 visit)- *Data collection of the CCB should not occur in Off-state. Tests should be administered in the following order:*

- HVLT-R (Trials 1-3)
- NAB Digits Forward
- NAB Digits Backward

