5.3 Justification for Treatment Protocol

The results from the single-site RCT provide evidence to support the safety and effectiveness of TNM™ Device treatments for managing the symptoms associated with PD, experienced by those that have PDD. TNM™ Device treatments in this study utilized the same time-varying waveform and BID schedule as was used in a pivotal study that demonstrated TNM™ is a safe and effective prophylactic for episodic migraine. The study described herein will utilize the same active treatment waveform and BID treatment regimen as were used in these previous studies.

In this study, participants will treat for 12 weeks (84 days) rather than 8 weeks (56 days), as was the case for the single-site RCT. The selection of a longer treatment interval was based on the finding that the treatment response, including measures of relevance to PDD, did not reach an asymptote during the 8 weeks of treatment. These results suggest that additional gains may be obtained with longer treatment intervals. Notably, 12-week treatment intervals were shown to be safe for the indication of episodic migraine, and there has been no evidence from a small crossover study in PD that treatment intervals of 12-16 weeks of treatments increases the risk of device-related AEs relative to 8 weeks. The treatment interval in this study will be limited to 12 weeks to minimize confounding variables that may arise with participants changing concomitant medications.

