5.4 End of Study Definition

Participants will continue to be enrolled in the study until at least 12 participants have been dispensed a study Device. The study will end when all study participants have completed their end

SHARPEN, V3.0 -- CONFIDENTIAL

Clinician version – not for patient use

of treatment (or early termination/withdrawal) visit or safety data support early termination of the study.

6 Study population

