2. STUDY DESIGN

This is a single arm study designed to evaluate the safety and feasibility of twice daily time-varying caloric vestibular stimulation (tvCVS) treatments using a solid-state Device developed by Scion NeuroStim, Inc. (SNS), also known as ThermoNeuroModulation (TNMTM), in patients with mild/moderate Parkinson's disease dementia (PDD) and to collect initial evidence to support proof of concept for the treatment of mild/moderate dementia in Parkinson's disease (PD). Participants will self-administer (with assistance, if necessary) ~19-minute *BID* treatments of tvCVS treatment over a period of 12 weeks (84 days). The study will be conducted at 2 centers located in the United States. This single-arm exploratory clinical trial will continue with competitive enrollment until 12 participants receive at least 1 treatment with the study Device at which point competitive enrollment will be closed.

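### Protocol 8.2.1 makes reaching target enrollment a mandatory withdrawal event, in conflict with the planned 84 days of treatment and the Day 84 endpoints

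*Protocol*

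**What the plan says.** Protocol 8.2.1 introduces its list with "Participants must be withdrawn from the clinical trial if any of the following events occur". The last item is "SNS discontinues the study or has achieved the targeted enrollment". Neither the item nor the surrounding text confines it to people who have not yet started treatment. The same section asks the investigator to try to complete the final-visit evaluations for anyone discontinued. It also removes early withdrawals from the per-protocol analysis.

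The target is defined elsewhere, and the only effect given there is that enrollment stops:

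- Protocol 1.1 (Synopsis): "This study will enroll participants until 12 participants have received at least one (1) treatment with the TNM™ Device prior to competitive enrollment closing". Protocol 10.1 uses the same criterion of 12 treated participants.
- SAP section 2: enrollment continues "until 12 participants receive at least 1 treatment with the study Device at which point competitive enrollment will be closed".
- Protocol 5.4 words the trigger by dispensation: "Participants will continue to be enrolled in the study until at least 12 participants have been dispensed a study Device".

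On duration, Protocol 5.1.1 has participants treating twice daily "for the full treatment period up until the scheduled end of treatment visit", and Protocol 5.3 gives the interval as 12 weeks (84 days). SAP 2.2 defines the primary safety endpoint as the change in summed MDS-UPDRS Parts I to III from Day 0 to Day 84, and adherence as a percentage of the twice-daily treatments in the 12-week period.

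**The concern.** The lead-in to 8.2.1 is mandatory and any one listed event is enough. The target is met when participant 12 has a first treatment, on Day 0. From that moment the text requires withdrawal of participant 12 and of everyone else who has not yet finished. A site that follows the clause cuts treatment short. A site that ignores it departs from the written protocol, and Protocol 9.3 requires deviations to be recorded and reported.

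Three things are at stake for those still on treatment: the Day 84 timing of the primary safety measure, the 12-week adherence period, and membership of the per-protocol set. The feasibility results would then partly describe an administrative rule instead of the participants or the device.

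**Working it through.** **Inputs from the documents.** Target of 12 treated participants (Protocol 1.1 and 10.1, SAP 2). Treatment for 84 days, twice daily (Protocol 5.1.1 and 5.3). End-of-treatment window of 5 days either side of Day 84 (Protocol 5.1.1). Go/no-go completion criterion of 75%, or 9 of 12 (Protocol 10.1, SAP 4).

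**Assumption.** The documents give no accrual rate. I take 12 first treatments spread evenly over T days and examine T from 30 to 730.

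**Step 1: the plan's own figures.** With no events in n completers, the Poisson upper 95% bound is −ln(0.05)/n. For n = 9 this is 2.996/9 = 0.333, and for n = 12 it is 2.996/12 = 0.250. Both match the stated 0.33 and 0.25, and 9/12 = 75%. The planned figures reproduce.

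**Step 2: participant 12 under the clause as written.** Planned sessions are 84 × 2 = 168. Withdrawn on Day 0, participant 12 can have at most 1/168 = 0.6% or 2/168 = 1.2% of them and cannot reach Day 84. SAP 6.1 requires at least 70% adherence and the regularly scheduled Day 84 visit for the per-protocol set, so participant 12 is out on both counts.

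**Step 3: the others.** Participant i starts on day T(i − 1)/11. When participant 12 starts, participant i has been on study T(12 − i)/11 days and has reached Day 84 only if this is at least 84. The best possible adherence, with no session missed, is the smaller of 1 and T(12 − i)/(11 × 84), with participant 12 as in Step 2.

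| Accrual time T (days, assumed) | Reach Day 84 | Best possible median adherence | Zero-event bound on Day 84 completers |
|---|---|---|---|
| 30 | 0/12 | 18% | none |
| 60 | 0/12 | 36% | none |
| 84 | 1/12 (8%) | 50% | above 1, uninformative |
| 120 | 4/12 (33%) | 71% | 0.75 |
| 180 | 6/12 (50%) | 99% | 0.50 |
| 270 | 8/12 (67%) | 100% | 0.37 |
| 308 | 9/12 (75%) | 100% | 0.33 |
| 365 | 9/12 (75%) | 100% | 0.33 |
| 730 | 10/12 (83%) | 100% | 0.30 |

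**Step 4: thresholds.** Participant 1 reaches Day 84 only if T ≥ 84. Nine completers require participant 9 to finish: 3T/11 ≥ 84, so T ≥ 308. If a visit on Day 79 counts, 3T/11 ≥ 79 gives T of about 290, and the 180-day row becomes 7/12. At no accrual time do all 12 reach Day 84, because participant 12 never does.

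**The case against.** The strongest reply is that the clause has a sensible meaning: when enrollment closes, people who have consented but not been treated are released. The documents do call people in screening participants (Protocol 6.5 and 9.2.1). With a screening window of up to 21 days and competitive enrollment at about two sites, such people may well exist when participant 12 is treated. The whole visit schedule also presupposes that the 12 continue.

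This reading is plausible, but the text does not state it and the context does not point to it. The same item covers the sponsor discontinuing the study, which plainly reaches treated participants. The paragraph after the list deals with final-visit evaluations and collecting the device. Screen failures have their own section, 6.5, which does not mention enrollment closing.

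The second reply is that data would survive. The Schedule of Events collects the MoCA and MDS-UPDRS Parts I to III at the end of treatment or early termination visit, and SAP 6.6.2 accepts an early termination MoCA. That stands: retention as the SAP defines it, and an intention-to-treat MDS-UPDRS change, could still be computed. They would be at shortened exposure, and someone withdrawn after a few days could count as retained.

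Whether four or more such withdrawals would fail the go/no-go criterion is also open. Protocol 10.1 asks for completion of the end of treatment visit. SAP 4 asks for the assessments needed for the secondary endpoint, then describes that as the MoCA at the end-of-treatment visit.

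**Conclusion.** The clause is defective as written. It conflicts with the passages where reaching 12 only closes enrollment, with the 84-day treatment plan, and with the Day 84 and 12-week endpoint definitions. Applied literally, it costs participant 12 at minimum. The number of others lost follows from an accrual time the documents do not give; under even accrual, Day 84 completers range from 0/12 (under 84 days) to 10/12 (730 days).

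A reader might infer four stronger things, none of which the documents support:

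- **That every participant would be withdrawn.** Anyone who finished Day 84 before participant 12 started is unaffected.
- **That the clause contradicts the end-of-study definition.** Protocol 5.4 says "The study will end when all study participants have completed their end", but the sentence continues over the page break to accept an early termination or withdrawal visit, so mass withdrawal would formally satisfy it.
- **That the primary endpoints would be destroyed.** No one would reach Day 84 only if accrual took less than about 84 days, and final-visit assessments would be attempted even then. With accrual of about a year, the last three participants would miss Day 84.
- **That the trial would be run this way.** Nothing suggests so. This is most likely a drafting error in a binding rule.

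**What to change.** Reconcile the targeted-enrollment clause in Protocol 8.2.1 with the Synopsis, sections 5.1.1, 5.3 and 10.1, and SAP sections 2 and 2.2. State which participants, if any, the clause concerns. In the same edit, make the trigger consistent, since Protocol 5.4 counts devices dispensed and the other places count participants treated. Which rule applies to participants on treatment is for the sponsor and investigators to settle. The SAP's Day 84 and 12-week definitions must then agree with the result.

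The cost is one clause in the protocol. If the reconciled text leaves treated participants on study to Day 84, the planned 168 sessions and the bounds of 0.25 and 0.33 stand unchanged.
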